Appendix 1. Abbreviations and Definitions

Term	Definition
AD	atopic dermatitis
ADSS	Atopic Dermatitis Sleep Scale
AE	adverse event: Any untoward medical occurrence in a patient or clinical investigation subject administered a pharmaceutical product that does not necessarily have a causal relationship with this treatment. An adverse event can therefore be any unfavorable and unintended sign (including an abnormal laboratory finding), symptom, or disease temporally associated with the use of a medicinal (investigational) product, whether or not related to the medicinal (investigational) product.
ALP	alkaline phosphatase
ALT	alanine aminotransferase
ANC	absolute neutrophil count
ANCOVA	analysis of covariance
AST	aspartate aminotransferase
AUC	area under the concentration curve
blinding/masking	
A single-blind study is one in which the investigator and/or his staff are aware of the treatment but the patient is not, or vice versa, or when the sponsor is aware of the treatment but the investigator and/his staff and the patient are not.
 
A double-blind study is one in which neither the patient nor any of the investigator or sponsor staff who are involved in the treatment or clinical evaluation of the subjects are aware of the treatment received.

BMI	body mass index
BSA	body surface area
CDLQI	Children's Dermatology Life Quality Index
CI	confidence interval
C_{max}	maximum concentration
CRF	case report form
CRP	clinical research physician: Individual responsible for the medical conduct of the study. Responsibilities of the CRP may be performed by a physician, clinical research scientist, global safety physician or other medical officer.
C-SSRS	Columbia Suicide Severity Rating Scale

CSR	clinical study report
CTCAE	Common Terminology Criteria for Adverse Events
DFI	Dermatitis Family Impact
DLQI	Dermatology Life Quality Index
DMC	data monitoring committee
EASI	Eczema Area and Severity Index
ECG	electrocardiogram
eCOA	electronic clinical outcome assessment
eCRF	electronic case report form
eGFR	estimated glomerular filtration rate
enroll	The act of assigning a patient to a treatment. Patients who are enrolled in the trial are those who have been assigned to a treatment.
Enter	Patients entered into a trial are those who sign the informed consent form directly or through their legally acceptable representatives.
ePRO	electronic patient-reported outcome
EQ-5D-Y	European Quality of Life-5 Dimensions-Youth version
ERB	ethical review board
ETV	early termination visit
GCP	good clinical practice
HBcAb	hepatitis B core antibody
HBsAg	hepatitis B surface antigen
HBV	hepatitis B virus
HCV	hepatitis C virus
HIV	human immunodeficiency virus
IB	Investigator's Brochure
ICF	informed consent form
ICH	International Council for Harmonisation
IDQOL	Infant's Dermatitis Quality of Life Index

IEC	International Eczema Council
IGA	Investigator’s Global Assessment
IGF-BP-3	Insulin-like Growth Factor Binding Protein-3
IL	interleukin
INR	international normalized ratio
Investigational product	A pharmaceutical form of an active ingredient or placebo being tested or used as a reference in a clinical trial, including products already on the market when used or assembled (formulated or packaged) in a way different from the authorized form, or marketed products used for an unauthorized indication, or marketed products used to gain further information about the authorized form.
IV	intravenous
IWRS	interactive web-response system
JAK	Janus kinase
LOCF	last observed carried forward
LSM	least squares mean
MACE	major adverse cardiovascular events
MedDRA	Medical Dictionary for Regulatory Activities
MI	myocardial infarction
MMR	measles, mumps, and rubella
MMRM	mixed-effects model of repeated measures
MRI	magnetic resonance imaging
NEA	National Eczema Association
NRI	nonresponder imputation
NRS	Numeric Rating Scale
PBPK	Physiologically Based Pharmacokinetic
PD	pharmacodynamics
PDE-4 inhibitor	phosphodiesterase type 4 inhibitor
PeDRA	Pediatric Dermatology Research Alliance
PGI-S-AD	Patient Global Impression of Severity–Atopic Dermatitis

PK	pharmacokinetic
POEM	Patient-Oriented Eczema Measure
PPD	purified protein derivative
PRISM	Parent-Reported Itch Severity Measure
PRO	patient-reported outcome
PROMIS	Patient-Reported Outcomes Measurement Information System
QD	once daily
QoL	quality of life
RA	rheumatoid arthritis
RNA	ribonucleic acid
SAE	serious adverse event
SAP	statistical analysis plan
SCORAD	SCORing Atopic Dermatitis
SUSAR	suspected unexpected serious adverse reaction
t_{1/2}	half life
TB	tuberculosis
TBL	total bilirubin level
TCNI	topical calcineurin inhibitor
TCS	topical corticosteroids
TEAE	Treatment-emergent adverse event: An untoward medical occurrence that emerges during a defined treatment period, having been absent pretreatment, or worsens relative to the pretreatment state, which does not necessarily have to have a causal relationship with this treatment.
TSH	thyroid-stimulating hormone
TSLP	thymic stromal lymphopoietin
TYK2	tyrosine kinase 2
ULN	upper limit of normal
vIGA-AD	validated Investigator's Global Assessment for Atopic Dermatitis
VTE	venous thromboembolic event (deep vein thrombosis or pulmonary embolism)

VZV varicella-zoster virus

WPAI-AD-CG Work Productivity and Activity Impairment Questionnaire: Atopic Dermatitis
Caregiver

Appendix 2. Clinical Laboratory Tests

Clinical Laboratory Tests

Hematology^{a,b}

Hemoglobin
Hematocrit
Erythrocyte count (RBC)
Absolute Reticulocyte Count
Mean cell volume
Mean cell hemoglobin
Mean cell hemoglobin concentration
Leukocytes (WBC)

Platelets

Absolute counts of:

Neutrophils, segmented
Neutrophils, juvenile (bands)

Lymphocytes

Monocytes

Eosinophils

Basophils

Urinalysis^{a,b,d}

Color
Specific gravity
pH
Protein
Glucose
Ketones
Bilirubin
Urobilinogen
Blood

Leukocyte esterase

Nitrite

Lipids^{a,c}

Total cholesterol
Low-density lipoprotein
High-density lipoprotein
Triglycerides

Clinical Chemistry^{a,b}

Serum Concentrations of:

Sodium
Potassium

Total bilirubin

Direct bilirubin
Alkaline phosphatase
Bone alkaline phosphatase^l
Alanine aminotransferase (ALT)
Aspartate aminotransferase (AST)
Blood urea nitrogen (BUN)
Creatinine
Cystatin C
Uric acid
Calcium
Glucose
Albumin
Total protein
Estimated glomerular filtration rate (eGFR)^e
Creatine phosphokinase (CPK)
Gamma-glutamyl transferase (GGT)

Other Tests^a

Hepatitis B Surface antigen (HBsAg)^f
Anti-Hepatitis B Core antibody (HBcAb)^f
HBV DNA^k
Anti-Hepatitis B Surface antibody (HBsAb)^f
Human immunodeficiency virus (HIV)^f
Hepatitis C antibody^{f,g}
Thyroid-stimulating hormone (TSH)
Exploratory storage samples (serum, plasma and mRNA)
Pregnancy Test^h
Gonadal hormone (estradiol for females, and testosterone for males)ⁱ
Serum immunoglobulin (IgG, and IgE)
IGF-1 and IGFBP-3
QuantiFERON®-TB Gold or T-SPOT®.TB^j
PPD (local testing)
Baricitinib plasma levels

Abbreviations: HBV = hepatitis B virus; IGFBP-3 = insulin-like growth factor binding protein-3; PPD = purified protein derivative; RBC = red blood cell; TB = tuberculosis; WBC = white blood cell.

- a Assayed by Sponsor-designated laboratory.
- b Unscheduled or repeat blood chemistry, hematology, and urinalysis panels may be performed at the discretion of the investigator, as needed.
- c Fasting lipid profile. Patients should not eat or drink anything except water for 4 to 12 hours (depending on age and weight as specified in Section 9.4.3) prior to test. If a patient attends these visits in a nonfasting state, this will not be considered a protocol violation.
- d Microscopic examination of sediment performed only if abnormalities are noted on the routine urinalysis.
- e For patients <18 years old, eGFR calculated by Bedside Schwartz 2009 formula. For patients ≥18 years old, eGFR calculated using the Chronic Kidney Disease Epidemiology Collaboration [CKD-EPI] Creatinine 2009 equation.
- f Test required at Visit 1 only to determine eligibility of patient for the study.
- g A positive hepatitis C antibody (Hep C antibody) result will be confirmed with an alternate hepatitis C method (HCV RNA).
- h For all females of childbearing potential, a serum pregnancy test will be performed at Visit 1 and a local urine pregnancy test will be performed at Visit 2 and at all subsequent study visits after Visit 3. If required per local regulations and/or institutional guidelines, pregnancy testing can occur at other times during the study treatment period.
- i Gonadal hormones will be collected for patients aged 8 to <18 years.
- j The QuantiFERON®-TB Gold test is the preferred alternative to the PPD test for the evaluation of TB infection. In countries where the QuantiFERON®-TB Gold test or T-SPOT® is available, either test may be used instead of the PPD TB test. The QuantiFERON®-TB Gold test may be performed locally or centrally; the T-SPOT® must be performed locally. If the QuantiFERON®-TB Gold test is indeterminate, 1 retest is allowed. If the retest is indeterminate, then the patient is excluded from the study.
- k HBV DNA testing will be done in those patients who are HBcAb+ at screening.
- l Collection of a sample for bone alkaline phosphatase may be requested by the Sponsor as a reflex test if the alkaline phosphatase result is high.

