- a An early termination visit should be conducted if a patient discontinues from the study before Visit 31. Visit 801 is the post-treatment follow-up visit, which occurs after the patient has been off IP for approximately 4 weeks. Patients who have permanently discontinued IP but remain in the study for more than 28 days without IP will only complete Visit 31/ET; Visit 801 (follow-up visit) is not required. Patient health outcomes assessments (POEM, CDLQI/IDQOL, DFI, PROMIS-Depression, PROMIS-Anxiety, EQ-5D-Y, WPAI-AD-CG) are collected for the early termination visit but are not collected at Visit 31.
- b Height will be measured using a stadiometer and Sponsor-provided instructions. Blood pressure readings will be collected using the appropriate size pediatric blood pressure cuffs.
- c The symptom-directed physical examination may be repeated at the investigator’s discretion any time a patient presents with physical complaints.

- d TB test(s) including PPD, QuantiFERON[®]-TB Gold, and T SPOT[®]. In countries where the QuantiFERON-TB Gold test or T-SPOT is available, either test may be used instead of the PPD TB test. The QuantiFERON-TB Gold test may be performed locally or centrally; the T-SPOT must be performed locally.
- e If PPD testing was chosen to test for TB, then the patient must return and PPD test read 48 to 72 hours after Visit 1 (post-PPD).
- f Only required for patients who have been prescribed sponsor-provided TCS. At Visit 28 and beyond, TCS will no longer be provided by the sponsor.
- g The following measures (POEM, CDLQI/IDQOL, DFI, PROMIS-Depression and Anxiety, EQ-5D-Y, WPAI-AD-CG, and palatability/acceptability as noted) should be completed prior to any clinical assessments being performed on days when study visits occur. The following measures are collected via daily diary and should be completed at the end of the patient's day: PGI-S-AD, Itch NRS, Skin Pain NRS, ADSS, PRISM, missed school days and TCS use.
- h Suicidal ideation and behavior subscales excerpt – Adapted for the assessment of 11 preferred ideation and behavior categories. The C-SSRS will only be collected in patients ≥ 7 years old.
- i The Self-Harm Follow-up Form is only required if triggered by the Self-Harm Supplement Form.
- j Clinical chemistry will include estimated glomerular filtration rate (eGFR, calculated using Bedside Schwartz 2009 formula) calculated by the central laboratory from serum creatinine.

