- a An early termination visit should be conducted if patient discontinues from the study before Visit 31. Visit 801 is the post-treatment follow-up visit, which occurs after the patient has been off IP for approximately 4 weeks. Patients who have permanently discontinued IP but remain in the study for more than 28 days without IP will only complete Visit 31/ET; Visit 801 (follow-up visit) is not required. Patient health outcomes assessments (POEM, CDLQI/IDQOL, DFI, PROMIS-Depression, PROMIS-Anxiety, EQ-5D-Y, WPAI-AD-CG) are collected for the early termination visit but are not collected at Visit 31.
- b Height will be measured using a stadiometer and Sponsor-provided instructions. Blood pressure readings will be collected using the appropriate size pediatric blood pressure cuffs.
- c The symptom-directed physical examination may be repeated at the investigator's discretion any time a patient presents with physical complaints.
- d TB test(s) including PPD, QuantiFERON[®]-TB Gold, and T SPOT[®]. In countries where the QuantiFERON-TB Gold test or T-SPOT is available, either test may be used instead of the PPD TB test. The QuantiFERON-TB Gold test may be performed locally or centrally; the T-SPOT must be performed locally.
- e If PPD testing was chosen to test for TB, then the patient must return and PPD test read 48 to 72 hours after Visit 1 (post-PPD).
- f For patients prescribed sponsor-provided TCS as background treatment. At Visit 28 and beyond, TCS will no longer be provided by the sponsor.
- g The following measures (POEM, CDLQI/IDQOL, DFI, PROMIS-Depression and Anxiety, EQ-5D-Y, and WPAI-AD-CG) should be completed prior to any clinical assessments being performed on days when study visits occur. The following measures are collected via daily diary and should be completed at the end of the patient's day: PGI-S-AD, Itch NRS, Skin Pain NRS, ADSS, PRISM, missed school days, and TCS use.
- h Suicidal ideation and behavior subscales excerpt – Adapted for the assessment of 11 preferred ideation and behavior categories. The C-SSRS will only be collected in patients ≥ 7 years old.
- i The Self-Harm Follow-up Form is only required if triggered by the Self-Harm Supplement Form.
- j Clinical chemistry will include estimated glomerular filtration rate (eGFR, calculated using Bedside Schwartz 2009 formula) calculated by the central laboratory from serum creatinine.

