- [41] Have screening laboratory test values, including thyroid-stimulating hormone (TSH), outside the reference range for the population or investigative site that, in the opinion of the investigator, pose an unacceptable risk for the patient's participation in the study.

Note: Patients who are receiving thyroxine as replacement therapy may participate in the study, provided stable therapy has been administered for ≥ 12 weeks and TSH is within the laboratory's reference range. Patients who are receiving stable thyroxine replacement therapy who have TSH marginally outside the laboratory's normal reference range may participate if the treating physician has documented that the thyroxine replacement therapy is adequate for the patient.

- [42] Have any of the following specific abnormalities on screening laboratory tests:

- a. AST or ALT ≥ 2 x upper limit of normal (ULN)
- b. alkaline phosphatase (ALP) ≥ 2 x ULN
Note: Patients may be allowed to enroll if there is no other evidence of liver, bone, or other abnormality but cases must be discussed and judged not clinically significant by Lilly Medical prior to enrollment.
- c. total bilirubin ≥ 1.5 x ULN
Note: Patients may be allowed to enroll if there is no other evidence of liver or other abnormality but cases must be discussed and judged not clinically significant by Lilly Medical prior to enrollment.
- d. hemoglobin < 10.0 g/dL (100.0 g/L)
- e. total white blood cell count < 2500 cells/ μ L ($< 2.50 \times 10^3$ / μ L or < 2.50 GI/L)
- f. neutropenia (absolute neutrophil count [ANC] < 1200 cells/ μ L) ($< 1.20 \times 10^3$ / μ L or < 1.20 GI/L)
- g. lymphopenia (lymphocyte count < 750 cells/ μ L) ($< 0.75 \times 10^3$ / μ L or < 0.75 GI/L)

- h. thrombocytopenia (platelets $<100,000/\mu\text{L}$) ($<100 \times 10^3/\mu\text{L}$ or $<100 \text{ G/L}$)
- i. estimated glomerular filtration rate (eGFR) $<60 \text{ mL/min/1.73 m}^2$ (eGFR, calculated using Bedside Schwartz 2009 formula).

Note: For cases with any of the aforementioned laboratory abnormalities (Exclusion Criteria [41] and [42]), the tests may be repeated during screening, and values resulting from repeat testing may be accepted for enrollment eligibility if they meet the eligibility criterion.

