8.1. Discontinuation from Study Treatment

8.1.1. Temporary Discontinuation from Study Treatment

In some circumstances, it may be necessary to temporarily interrupt treatment as a result of AEs or abnormal laboratory values that may have an unclear relationship to IP. For example, IP should be temporarily interrupted if the patient experiences a cardiovascular adverse event considered to be related to study treatment, is graded as moderate (Grade 2 according to Common Terminology Criteria for Adverse Events [CTCAE] Version 3.0), and that does not resolve promptly with supportive care. Except in cases of emergency, it is recommended that the investigator consult with Lilly (or its designee) before temporarily interrupting therapy for reasons other than those defined in [Table JAIP.5](#).

For the abnormal laboratory findings and clinical events (regardless of relatedness) listed in [Table JAIP.5](#), specific guidance is provided for temporarily interrupting treatment and when treatment may be restarted. Retest frequency and timing of follow-up laboratory tests to monitor the abnormal finding is at the discretion of the investigator. Investigational product that was temporarily interrupted because of an AE or abnormal laboratory value not specifically covered in [Table JAIP.5](#) may be restarted at the discretion of the investigator.

Table JAIP.5. Criteria for Temporary Interruption of Investigational Product

Hold Investigational Product if the Following Laboratory Test Results or Clinical Events Occur:	Investigational Product May Be Resumed When:
WBC count <2000 cells/ μ L (<2.00x10 ³ / μ L or <2.00 GI/L)	WBC count \geq 2500 cells/ μ L (\geq 2.50x10 ³ / μ L or \geq 2.50 GI/L)
ANC <1000 cells/ μ L (<1.00x10 ³ / μ L or <1.00 GI/L)	ANC \geq 1200 cells/ μ L (\geq 1.20x10 ³ / μ L or \geq 1.20 GI/L)
Lymphocyte count <500 cells/ μ L (<0.50x10 ³ / μ L or <0.50 GI/L)	Lymphocyte count \geq 750 cells/ μ L (\geq 0.75x10 ³ / μ L or \geq 0.75 GI/L)
Platelet count <75,000/ μ L (<75x10 ³ / μ L or <75 GI/L)	Platelet count \geq 100,000/ μ L (\geq 100x10 ³ / μ L or \geq 100 GI/L)
eGFR <50 mL/min/1.73 m ² (from serum creatinine)	eGFR \geq 60 mL/min/1.73 m ²
ALT or AST >5x ULN	ALT and AST return to <2x ULN, and IP is not considered to be the cause of enzyme elevation
Hemoglobin <8 g/dL (<80.0 g/L)	Hemoglobin \geq 10 g/dL (\geq 100.0 g/L)
Symptomatic herpes zoster (shingles or chicken pox)	All skin lesions have crusted and are resolving

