10.3.4. Safety Analyses

All safety data will be descriptively summarized by treatment group and analyzed using the safety population.

Treatment-emergent adverse events (TEAEs) are defined as AEs that first occurred or worsened in severity after the first dose of study treatment. The number and percentage of patients who experienced at least 1 TEAE will be summarized using MedDRA (Medical Dictionary for Regulatory Activities) for each Preferred Term within System Organ Class by treatment group. Serious adverse events and AEs that led to permanent discontinuation from the IP will also be summarized by treatment group. Special safety topics will be summarized and analyzed including the proportion and rate of patients developing skin infections requiring antibiotic treatment. Fisher’s exact test will be used to perform comparisons between each baricitinib dose and the placebo group, where applicable.

Clinical laboratory results will be descriptively summarized by treatment group. Individual results that are outside of normal reference ranges will be flagged in data listings. Quantitative clinical laboratory variables obtained at baseline and postbaseline visits will be summarized along with change from baseline by treatment group. Change from baseline to endpoint will be analyzed using ANCOVA with treatment and baseline value in the model. Categorical variables, such as treatment-emergent laboratory abnormalities, will be summarized by frequency and percentage. Shift tables will be presented for selected laboratory measures.

Observed values and changes from baseline for vital signs and physical characteristics will be descriptively summarized by treatment group and time point. Change from baseline to postbaseline in vital signs, height, and body weight will be analyzed using ANCOVA with treatment and baseline value in the model. Treatment-emergent abnormalities in vital signs (pulse and blood pressure) and weight will be evaluated based on pediatric standards.

A summary of temporary interruptions of study drug will be provided, showing the number of patients experiencing at least one temporary interruption and the number of temporary interruptions. Duration of each temporary interruption and the cumulative duration of interruptions using descriptive statistics will be provided.

Analyses of Growth (height, weight, and body mass index [BMI]):

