Appendix 2. Clinical Laboratory Tests

Clinical Laboratory Tests**Hematology^{a,b}**

Hemoglobin
 Hematocrit
 Erythrocyte count (RBC)
 Absolute Reticulocyte Count
 Mean cell volume
 Mean cell hemoglobin
 Mean cell hemoglobin concentration
 Leukocytes (WBC)

Platelets

Absolute counts of:

Neutrophils, segmented
 Neutrophils, juvenile (bands)

Lymphocytes

Monocytes

Eosinophils

Basophils

Urinalysis^{a,b,d}

Color
 Specific gravity
 pH
 Protein
 Glucose
 Ketones
 Bilirubin
 Urobilinogen
 Blood

Leukocyte esterase

Nitrite

Lipids^{a,c}

Total cholesterol
 Low-density lipoprotein
 High-density lipoprotein
 Triglycerides

Clinical Chemistry^{a,b}**Serum Concentrations of:**

Sodium
 Potassium

 Total bilirubin

 Direct bilirubin
 Alkaline phosphatase
 Bone alkaline phosphatase^l
 Alanine aminotransferase (ALT)
 Aspartate aminotransferase (AST)
 Blood urea nitrogen (BUN)
 Creatinine
 Cystatin C
 Uric acid
 Calcium
 Glucose
 Albumin
 Total protein
 Estimated glomerular filtration rate (eGFR)^e
 Creatine phosphokinase (CPK)
 Gamma-glutamyl transferase (GGT)

Other Tests^a

Hepatitis B Surface antigen (HBsAg)^f
 Anti-Hepatitis B Core antibody (HBcAb)^f
 HBV DNA^k
 Anti-Hepatitis B Surface antibody (HBsAb)^f
 Human immunodeficiency virus (HIV)^f
 Hepatitis C antibody^{l,g}
 Thyroid-stimulating hormone (TSH)
 Exploratory storage samples (serum, plasma and mRNA)
 Pregnancy Test^h
 Gonadal hormone (estradiol for females, and testosterone for males)ⁱ
 Serum immunoglobulin (IgG, and IgE)
 IGF-1 and IGFBP-3
 QuantiFERON®-TB Gold or T-SPOT®.TB^j
 PPD (local testing)
 Baricitinib plasma levels

Abbreviations: HBV = hepatitis B virus; IGFBP-3 = insulin-like growth factor binding protein-3; PPD = purified protein derivative; RBC = red blood cell; TB = tuberculosis; WBC = white blood cell.

- ^a Assayed by Sponsor-designated laboratory.
- ^b Unscheduled or repeat blood chemistry, hematology, and urinalysis panels may be performed at the discretion of the investigator, as needed.
- ^c Fasting lipid profile. Patients should not eat or drink anything except water for 4 to 12 hours (depending on age and weight as specified in Section 9.4.3) prior to test. If a patient attends these visits in a nonfasting state, this will not be considered a protocol violation.
- ^d Microscopic examination of sediment performed only if abnormalities are noted on the routine urinalysis.
- ^e eGFR calculated by Bedside Schwartz 2009 formula.

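### The protocol gives two eGFR equation rules for patients who reach 18, and its fixed renal hold and resume thresholds do not say which one applies

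*Protocol*

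**What the plan says.** Five places in the protocol bear on how eGFR is computed and used.

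- **Section 2, Tables JAIP.1 and JAIP.2, footnote j.** Both schedules carry the same sentence: "Clinical chemistry will include estimated glomerular filtration rate (eGFR, calculated using Bedside Schwartz 2009 formula) calculated by the central laboratory from serum creatinine". It has no age limit, and chemistry is scheduled through Visit 31 and the follow-up visit.
- **Main Appendix 2, footnote e.** This splits by age: "For patients <18 years old, eGFR calculated by Bedside Schwartz 2009 formula", and then "For patients ≥18 years old, eGFR calculated using the Chronic Kidney Disease Epidemiology Collaboration [CKD-EPI] Creatinine 2009 equation".
- **Appendix 12.2, country-specific copy of Appendix 2, footnote e.** Only "eGFR calculated by Bedside Schwartz 2009 formula", with no second equation.
- **Section 8.1.1, Table JAIP.5.** Treatment is held at "eGFR <50 mL/min/1.73" m² and may resume at 60 or above. The table says the value comes from serum creatinine but names no equation.
- **Section 10.3.4.** For quantitative laboratory variables, "Change from baseline to endpoint will be analyzed using ANCOVA with treatment and baseline value in the model". eGFR is one of the chemistry results listed in Appendix 2.

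The exclusion criterion on eGFR in Section 6.2 also names Bedside Schwartz ("eGFR, calculated using Bedside Schwartz 2009 formula"). That raises no conflict, because every patient is under 18 at entry.

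**The concern.** A fixed threshold on a derived quantity is defined only if the derivation is. Patients enter at 2 to under 18 years (Section 6.1) and may continue in the extension for up to 5 more years (Section 5.1.4). Appendix 6 expects some to turn 18 on study. For such a patient the schedules point to one equation and the main Appendix 2 to another. The two equations can fall on opposite sides of the Table JAIP.5 thresholds for one creatinine value. Section 5.5 describes renal elimination as the principal mechanism of clearance, so this is a relevant safety measure.

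There is also a consequence for the analysis. If footnote e is followed as written, a patient who passes 18 has a Schwartz baseline and a CKD-EPI follow-up value. The change from baseline then contains a step that comes from the change of equation and not from kidney function.

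**Working it through.** The protocol states no eGFR figure that could be reproduced. The check has two parts: compare the texts, then size the gap between the two named equations.

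**1. Texts, for a patient aged 18 or over**

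| Place | Equation |
|---|---|
| Schedules, footnote j (both) | Bedside Schwartz, no age limit stated |
| Main Appendix 2, footnote e | CKD-EPI 2009 |
| Appendix 12.2 copy, footnote e | Bedside Schwartz |
| Table JAIP.5 | none named |

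This contradiction rests on the documents alone.

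**2. Size (assumption)**

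The protocol names the equations but prints neither. The coefficients below are assumed to be the published ones, with creatinine (Scr) in mg/dL and height in cm:

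- Bedside Schwartz = 0.413 × height / Scr
- CKD-EPI 2009 = 141 × min(Scr/k, 1)^a × max(Scr/k, 1)^−1.209 × 0.993^age, multiplied by 1.018 if female. For males k = 0.9 and a = −0.411; for females k = 0.7 and a = −0.329. The race term is left out; including it (× 1.159) raises the CKD-EPI value further.

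At age 18, 0.993^18 = 0.881, so the leading constant is 141 × 0.881 = 124.3 for males and 124.3 × 1.018 = 126.5 for females.

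*At the hold boundary (Schwartz = 49.9).*

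- Male, 175 cm: Scr = 0.413 × 175 / 49.9 = 1.448. CKD-EPI = 124.3 × (1.448/0.9)^−1.209 = 124.3 × 0.563 = 69.9.
- Female, 165 cm: Scr = 0.413 × 165 / 49.9 = 1.366. CKD-EPI = 126.5 × (1.366/0.7)^−1.209 = 126.5 × 0.446 = 56.4.

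Over a range of heights, for a patient just under 50 by Schwartz:

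| Patient | CKD-EPI at the same creatinine |
|---|---|
| Male up to about 198 cm | 60 or above |
| Female up to about 156 cm | 60 or above |
| Female about 157–182 cm | 50 to 60 |
| Female above about 183 cm, or male above about 231 cm | below Schwartz |

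*At ordinary, unchanged creatinine.*

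| Male 176 cm, Scr | Schwartz | CKD-EPI | Change |
|---|---|---|---|
| 0.6 | 121.1 | 146.8 | +25.6 |
| 0.8 | 90.9 | 130.4 | +39.6 |
| 0.9 | 80.8 | 124.3 | +43.5 |
| 1.1 | 66.1 | 97.5 | +31.4 |

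| Female 163 cm, Scr | Schwartz | CKD-EPI | Change |
|---|---|---|---|
| 0.5 | 134.6 | 141.3 | +6.7 |
| 0.7 | 96.2 | 126.5 | +30.3 |
| 0.9 | 74.8 | 93.3 | +18.5 |

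**3. When it arises**

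Suppose, as an assumption, that the 320 older patients have ages spread evenly over 10 to under 18. About (16/52)/8 × 320 = 12 would then turn 18 within the 16-week controlled period. The effect therefore falls mainly in Period 4.

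**The case against.** The strongest reply is that this is shorthand and not conflict. Section 9.4.3 sends the reader to Appendix 2 for the tests and to the schedule for timing. Footnote e is the more specific rule, and footnote j is silent on age without actually saying that Schwartz applies at every age. The central laboratory does the calculation, so sites do not choose. Appendix 12.2 says its purpose is pregnancy testing and benefit-risk wording, so its footnote e looks like a copy that was not updated and not a deliberate country rule. This is a plausible account of what was intended, but it does not settle the text. In the same footnote lists the sponsor writes age limits where it wants them (imaging stops at 18; gonadal hormones for ages 8 to under 18). Table JAIP.5 names no equation, and no passage says which footnote prevails.

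A second reply is that handling of derived variables belongs to the SAP. That is fair as to detail, and the absence of an instruction is not the point here. The point is that footnote e, followed literally, creates the mixed-equation change.

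Three stronger readings are tempting, and the documents do not support them.

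- *A birthday could put a patient on hold.* On the assumed coefficients this needs a female above about 183 cm or a male above about 231 cm, so that direction is nearly empty.
- *A hold would be released, or a real decline concealed, by the equation alone.* Resumption in Table JAIP.5 is permissive, and investigators must document their review of each laboratory safety report (Section 9.2). Many females would leave the hold range without reaching 60. Creatinine is itself a listed analyte, so its change from baseline is already covered by Section 10.3.4.
- *Large numbers would be affected over five years.* Section 5.1.4 makes Visit 27 the last treatment visit for patients aged 12 or over unless the sponsor approves otherwise in writing. Nothing in the protocol says how often an eGFR near 50 would coincide with an 18th birthday.

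**Conclusion.** The point holds in this limited form. For patients aged 18 or over, the protocol gives two incompatible statements of the eGFR equation, and the Table JAIP.5 thresholds rest on a value that is therefore not uniquely defined. One creatinine can meet the hold under the schedules and the Appendix 12.2 copy, and not meet it under the main Appendix 2. Under footnote e, eGFR change from baseline also combines two equations within a patient, with a step of about +26 to +44 mL/min/1.73 m² (176-cm male, creatinine 0.6–1.1 mg/dL) or +7 to +30 (163-cm female, 0.5–0.9 mg/dL) at unchanged creatinine.

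The contradiction needs no outside figure. The sizes rest on coefficients and heights that the protocol does not give. The primary efficacy analysis is not affected, and randomization gives no reason to expect the step to differ between arms in the controlled period. The issue is worth correcting because it touches a treatment-hold rule and long-term renal safety reporting. No view is taken on which equation or threshold is clinically right.

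**What to change.** 1. Reconcile footnote j in Tables JAIP.1 and JAIP.2, footnote e in the main Appendix 2, footnote e in the Appendix 12.2 copy, and Table JAIP.5, so that one stated rule defines the eGFR used for the hold and resume thresholds at every age. The choice of equation is the sponsor's.
2. State, in the protocol or the SAP, that eGFR change from baseline and eGFR shifts use the same equation at baseline and post-baseline within each patient. Read the result beside the creatinine change that Section 10.3.4 already covers.

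The cost is footnote wording and one derived variable. Creatinine and height are already collected, so no new samples are needed. The drawback is that, for this analysis only, one equation is applied outside its usual age range in patients who cross 18.
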